### **8.3.2 Incidental Findings**

Participants will have the option to consent for any incidental findings to be shared with their primary care provider. If there is an incidental finding deemed by the PI to be clinically

---

relevant, the primary care provider will be notified. The parent/guardian will be notified and asked to follow up with the subject's primary care provider if during the visit; a subject is noted to have blood pressure that is  $\geq$  the 95th percentile for age, gender, and height. We will notify the parent/guardian/primary care provider with clinically relevant abnormal labs. Specifically, lipid levels/insulin levels/blood glucose levels/OGTT results/TSH and T4. Note that some labs, such as lipids and insulin, are run in batches and reporting of results may be delayed.

### 8.3.3 Risk Assessment

The risks of participating in this study are relatively small and the investigators believe the overall study is of minimal risk to the participants. An OGTT will only be administered to subjects that have BMIs  $\geq$  85th percentile, not known to have diabetes.

Expected risks to the subject are as follows:

- Blood draw may result in temporary discomfort from the needle stick, bruising, fainting, weakness, and rarely an infection at the site
- Possible side effects of the OGTT include temporary high or low blood sugar and upset stomach
- Anthropometric measurements and pubertal status exam poses minimal risks
- Exposure to radiation during DXA scan
- Sharing of private health information (PHI) including dietary intake, demographic information, health history and medical information
- Pulse wave velocity and pulse wave analysis poses minimal risks
- 12 hour overnight fasting may cause hunger pangs, upset stomach, headache, or lightheadedness
- Blood pressure measurement by auscultation may cause temporary numbness/tingling in the arm
- SenseWear® Armbands worn for 7 consecutive days may cause skin irritability
- Sensitive psychosocial issues may arise during questionnaire assessment

A small amount of blood (about 3 teaspoons) will be drawn at major assessment points. Adolescents may experience some degree of discomfort, bruising, or lightheadedness with fasting blood draws. There is also a risk of infection when blood is drawn. These occurrences are rare, generally mild, and respond to conservative treatment.

The OGTT is frequently used to screen for diabetes and impairments in glucose regulation in children both within the confines of a study and in routine clinical practice; additional intermediate blood draws will be performed for glucose and insulin in order to assess insulin sensitivity. Because of these intermediate time points for blood collection, an intravenous line will be placed, which can be associated with discomfort and a small risk of infection. The use of EMLA cream is optional to minimize discomfort to the study participant. Experienced pediatric research nurses will perform the OGTT; OGTT are routinely performed in this setting. Seven blood samples are required and the volumes of blood will be minimized to reduce the risk of anemia. The concern with OGTT is hypoglycemia occurring 2-3 hours after consumption of the dextrose load. If hypoglycemic

---

symptoms develop, blood glucose will be checked. In the event of hypoglycemia (blood glucose < 60 mg/dL), the study will be terminated and carbohydrates consumed by the subject. Blood glucose will be monitored until normalization is assured. To minimize subject burden, particularly in this cohort of children with developmental disabilities, we will perform OGTT only in subjects with BMI ≥ 85%. While the aim of the study is to uncover cardiometabolic risk factors in children with DS and to uncover whether adolescents with DS have greater risk for a given BMI z-score, glucose intolerance is unlikely in children with BMI < 85% and the yield of doing OGTT in this subgroup is relatively low. Our team felt that it was crucial to be sensitive to the burden of participation placed on these children with intellectual and developmental disabilities and their families.

Participation in the study involves risks associated with the small amount of radiation exposure associated with the DXA whole body scan for body composition assessment; the total radiation EDE from DXA scans is less than 3 μSv (or 1 mrem). This total amount of radiation is less than the exposure to daily background radiation at sea level (3,000 μSv per year) and is therefore considered minimal risk. Females of childbearing potential undergo a urine pregnancy test prior to the DXA scans. Pregnant females do not have DXA scans performed in order to protect the unborn fetus.

The anthropometric assessment involves measurements of height, weight, circumferences and skinfold thickness. There is a very minor possibility of bruising from the skinfold thickness measurements. The exam will be performed by trained anthropometrists experienced in obtaining measurements in children at all levels of cognitive ability. The measurements are obtained in a private room. The parent is permitted to stay with the child if it increases their comfort with the exam.

The puberty assessment will be performed by pediatric endocrinologists in a private setting. The procedure will be explained to the child in advance, and the parent is permitted to be present if preferred by the child. The exam is performed by highly experienced personnel who are familiar with minimizing distress associated with the exam.

SenseWear® Armbands (Body Media, Inc.). There is little to no risk associated with measuring physical activity, sedentary behavior, and sleep with armband accelerometers. These accelerometers fit comfortably on the participant's arm and can easily be removed should he/she become uncomfortable. Some patients may experience skin irritation, particularly when sweating, with the devices in which case they can adjust them or in rare instances, remove them if necessary. To prevent irritation, parents will be instructed to clean the armband with mild soap and water when the child removes it to bathe or shower. If irritation does occur, parents will be instructed to use Aquaphor or Vaseline where the fabric of the band is to treat and prevent further irritation. If a child is allergic to metal they will not be required to complete this assessment.

A licensed clinical psychologist with expertise in working with children and adolescents, will meet with families concerning sensitive psychosocial issues that may arise during assessments or intervention. Any emotional upset will be handled with appropriate support to the participants and their caregivers. Further, if a behavioral health concern arises

---

during the study needing further evaluation and treatment, the clinical psychologist will assist with a referral.

If a subject shows any signs of clinical instability or definitively decides to discontinue participation, the study visit will end.

#### **8.3.4 Potential Benefits of Study Participation**

There may be no direct benefit and benefits will be to future patients, Science and society. Participants may directly benefit from identification of abnormalities such as diabetes from the OGTT. Participants may indirectly benefit from identification of abnormalities such as dyslipidemia and hypothyroidism from the fasting blood draw. If clinically relevant abnormalities are found, the family will be notified. With the consent from the family, clinically relevant tests results will be shared with the subject's primary care physician. Only studies performed by CLIA certified labs will be disclosed. Participants found to have an impaired fasting glucose or impaired glucose tolerance will be referred appropriately for further management and treatment.

The physical activity questionnaires and dietary recall may potentially lead the participants/parents/guardians into awareness about making healthy lifestyle options in diet and exercise.

There is also a potential indirect benefit in helping scientists and health providers further understand the relationship between obesity and Cardiometabolic risk in Down syndrome youth.

#### **8.3.5 Risk-Benefit Assessment**

The benefits to participation in this trial outweigh the potential risks. Clinicians caring for obese adolescents with Down syndrome with or without CHD have very little scientific evidence upon which to base guidance regarding Cardiometabolic risk. Data regarding prevalence of pre-diabetes and T2D and on CVD risk in obese adolescents with Down syndrome are lacking. This study will have direct implications for the daily medical care of individuals with Down syndrome. Currently, we do not know whether BMI is the best marker of cardiometabolic risk in Down syndrome. We plan to determine which measure of adiposity best captures CVD and or diabetes risk in Down syndrome, so that primary care providers will know what measure to use to assess risk in adolescents with Down syndrome (i.e. BMI, waist circumference, or skin fold thickness). Medical providers will then be able to use the appropriate measure for prevention, and to guide screening.

### **8.4 Recruitment Strategy**

Potential subjects will be identified using the protocol inclusion and exclusion criteria. Subjects will be recruited from multiple sources, including local primary care, Endocrinology, Cardiology and Trisomy 21 clinics, local advertisements, previous studies (if they gave permission to be contacted), and DS community events. The DS Connect recruitment registry will e-mail registry participants the IRB-approved recruitment flyer.

A study website will also be used as a source of information for potential DS and control subjects.

The Recruitment Enhancement Core (REC) will e-mail or postal mail potential control subjects using the IRB-approved REC letter for control subjects. This letter will contain opt-out language that allows study staff to contact participants via one phone call who have not opted-out 2 weeks following the letter being sent.

After the initial telephone screening, subjects that agree to participate and qualify for the study will be scheduled for an appointment. Verbal consent will be obtained by the study team prior to the screening.

### **8.5 Informed Consent/Assent and HIPAA Authorization**

Prior to conducting the screening interview and prior to mailing the family the HFI questionnaire, verbal consent from the subject (if 18 years or older)/parent/guardian/legal authorized representative will be obtained and documented by the study coordinator/study investigator. A description of the procedures involved in the study, as well as the risks/benefits will be provided verbally as part of this process. Additionally, it will be stressed that any questions are appropriate and that all aspects of the study are voluntary.

Prior to conducting the study visit procedures, the study coordinator will obtain consent and if appropriate assent from the participant. A waiver of minor assent by the study coordinator will be obtained for participants not capable of assenting. The consent/assent process will take place in a private room. It will be stressed again that participation in the study is voluntary and that any questions can and should be raised. Consent and assent will be documented by the parent/guardian/participant's signatures on the approved consent documents. A description of the procedures involved in the study, as well as the risks and benefits, will be provided verbally as part of the consent process.

Consent/assent documents will be maintained in the participant's study file and documented. The parent/guardian will receive a copy of the signed document(s).

#### **8.5.1 Consent for Down syndrome subjects 18 – 20 years of age**

Ability to provide consent will be ascertained by the study team. Initially, the team will assess the participants' ability by engaging them in conversation to obtain a brief, general sense of their ability to comprehend and communicate. If ability to provide consent seems likely, the team will then explain the following to confirm that the study participant understands all of the essential elements of the consent form:

- a. The purpose of the research study. We will explain that the study is trying to find out which tests and measurements will best capture the risks of heart disease and type 2 diabetes in children and adolescents with DS. We will ask them to explain in their own words what the study is about.

- 
- b. Study procedures will be explained with the aid of a picture book that depicts the study visit and at-home procedures. We will then ask them to explain in their own words what each procedure will be like.
  - c. The staff will clearly explain that the study participant does not have to participate in the study, that they can change their mind about being in the study at any time, and that no one will be disappointed, upset or consider it a failure if they decide they do not want to continue with the study. Subjects will be asked to explain in their own words that they understand that they do not have to participate in the study and that there are no consequences if they choose not to.
  - d. We will explain that their information will be kept private to the best of our ability. We will explain the risks of each procedure. We will also explain that they may learn more about their health from the study, and that their health may improve from taking the thyroid hormone pills, but that it is also possible that they may not benefit from the study. Participants will be asked to explain in their own words what they understand about the risks and benefits of the study.

If it is deemed by the study team at any of the above points that the subject is unable to consent for themselves, the subject's legally authorized representative/health care representative will provide the written informed consent on the subject's behalf.

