## **3 INVESTIGATIONAL PLAN**

### **3.1 General Schema of Study Design**

This observational cross-sectional study will involve one study visit for all groups. All participants will be consented before any procedures. During the study visit both groups will receive: urine pregnancy test (for female subjects), fasting blood sample, OGTT (if BMI $\geq$ 85% percentile), DXA scan, anthropometric measurements, pubertal status exam, PWV and PWA, echocardiography, family history of CVD/dyslipidemia/T2DM, QOL, body image, eating behaviors and other questionnaires. Three twenty-four hour dietary recall interviews of parents and children will be conducted by research bionutritionists by telephone, using the multi-pass method. Accelerometers will be distributed for home use.

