### **4.3 Subject Completion/Withdrawal**

Subjects may withdraw from the study at any time without prejudice to their care. They may also be discontinued from the study at the discretion of the investigators for lack of adherence to study treatment or visit schedules, AEs, and/or pregnancy. The investigators may also withdraw subjects who violate the study plan, or to protect the subject for reasons of safety or for administrative reasons. It will be documented whether or not each subject completes the clinical study. If the Investigators become aware of any serious, related adverse events after the subject completes or withdraws from the study, they will be recorded in the source documents and on the CRF.

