### **7.2 Adverse Event Reporting**

The Investigator is responsible for recording and reporting unanticipated problems related to research that occur during and after study treatment. The plan for Adverse Event reporting should be consistent with the study site IRB Guidelines. Since the study procedures are not greater than minimal risk, SAEs are not expected. If any unanticipated problems related to the research involving risks to subjects or others happen during the course of this study (including

---

SAEs) these will be reported to the IRB in accordance with the study site policies. AEs that are not serious but that are notable and could involve risks to subjects will be summarized in narrative or other format and submitted to the IRB at the time of continuing review.

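### The consent script for 18–20-year-olds with Down syndrome describes a benefit from thyroid hormone pills that this observational study does not give

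*Combined protocol and SAP*

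**What the plan says.** Section 8.5.1 of the combined protocol and SAP sets out how staff decide whether a participant with DS aged 18–20 can consent. After a short first conversation, "If ability to provide consent seems likely, the team will then explain the following", and four items (a to d) follow. They cover the purpose, the procedures, the freedom to decline, and finally privacy, risks and benefits. Each of the purpose, procedures, freedom and risk-benefit parts ends with the participant restating the content. If the team judges at any of these points that the person cannot consent, a legally authorized representative signs instead.

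Item d has staff say that "their health may improve from taking the thyroid hormone pills". The same sentence adds a caveat: "but that it is also possible that they may not benefit from the study".

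Other sections describe a study without treatment. Section 3.1 states: "This observational cross-sectional study will involve one study visit for all groups". Section 8.3.4 opens its account of benefits with "There may be no direct benefit and benefits will be to future patients, Science and society" and, on thyroid disease, says only that "Participants may indirectly benefit from identification of abnormalities such as dyslipidemia and hypothyroidism from the fasting blood draw".

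**The concern.** The clause speaks of the pills as though they were part of taking part, and no other section supplies them. Staff who follow it would describe to adults with intellectual disability a treatment benefit that the study cannot provide.

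Its position makes this worse. Item d is one of four teach-back items on which the capacity judgement rests. A participant could repeat a false benefit and be taken to understand. Another could say, correctly, that the study gives no pills and be taken not to. The described benefit also has no matching risk, because the risk assessment in section 8.3.3 lists none for thyroid hormone.

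What is at stake is the accuracy of consent in a vulnerable group. The scientific results are not at stake.

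**Working it through.** The plan gives no figure to reproduce on this point. The check sets item d against every part of the document where a study drug would have to appear.

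| Place | What it contains |
|---|---|
| Synopsis (Study Design) and section 3.1 | Cross-sectional, observational, two groups, one visit; no treatment arm |
| Table 1 (schedule) | TSH and T4 as a blood test; no thyroid hormone or other study drug |
| Sections 4.1 to 4.2 (procedures, follow-up) | Measurements, questionnaires, an armband and diet recalls. The glucose drink for the OGTT is the only substance taken for a test |
| Section 5.1.3 (laboratory list) | TSH and T4 measured |
| Section 5.1.8 (safety evaluation) | Newly found conditions are referred to the pediatrician; topical anesthetic, and glucose for low blood sugar |
| Sections 8.3.1 and 8.3.2 | Families or primary care are told of relevant abnormal results, including TSH and T4 |
| Section 8.3.3 (risks) | No thyroid hormone risk |
| Section 8.3.4 (benefits) | Possible detection of abnormalities, referral of those with impaired glucose results, lifestyle awareness, benefit to science; no pill benefit |

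Thyroid hormone is not provided, prescribed, dosed or scheduled anywhere. Apart from item d, thyroid treatment appears only in titles in the reference list.

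Two readings that might rescue the clause fail.

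- **Treatment after referral.** The sentence mentions no test result, diagnosis or referral, and it is addressed to everyone who reaches item d.
- **Another part of the study.** The synopsis labels its objectives as Part 1 and marks efficacy as not applicable to Aim 1, which hints at a part not described here. No such part is defined, and section 3.1 gives every group one visit.

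Treatment wording also survives elsewhere. Section 4.3 allows discontinuation for "lack of adherence to study treatment or visit schedules", section 7.2 covers problems "that occur during and after study treatment", section 8.3.1 speaks of compliance with a treatment, and section 8.3.3 mentions an intervention. No treatment is defined in any of them. This suggests text carried over from another protocol or study part, but that is an inference.

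**How many people would hear it.** The documents give neither the age distribution nor the share who reach item d, so the count below is illustrative.

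- Inputs: 155 evaluable DS participants and ages 10 to 20 (Synopsis, section 3.2.2).
- Assumption: ages evenly spread over 11 age-years, of which 18, 19 and 20 are 3.
- Aged 18–20 among evaluable participants: 155 × 3/11 = 42.3, about 42.
- Reaching item d (assumed shares): 25% gives 10.6, about 11; 50% gives 21.1, about 21; 75% gives 31.7, about 32.
- If the base were instead the roughly 200 children with DS to be screened (section 6.1): 200 × 3/11 = 54.5, about 55. Not all of those screened would come to a consent visit.

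**The case against.** The strongest reply concedes that the clause is wrong but disputes its weight. The rest of the script describes the study correctly. Item a presents it as a search for the tests and measurements that best capture risk, and item b walks through each procedure with a picture book. Section 8.5 separately requires a spoken account of procedures, risks and benefits. Staff have no pills to hand out and might notice the error. Item d sets no scoring rule tied to the pills. The consent form, which participants sign, was not available and may be correct.

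Part of this stands. A participant misjudged because of the pill clause is a possible outcome, not a certain one, and the finding covers only what the protocol directs. The headcount is weak: 42 is a ceiling only for evaluable participants under an even age spread, and because consent precedes evaluability the true number could be higher or lower. The phrases in sections 4.3, 7.2, 8.3.1 and 8.3.3 tell participants nothing false, so correcting them is tidying.

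The core is untouched. The caveat makes the benefit uncertain without telling anyone that no pills will be given. An accurate consent form would not repair the protocol either: item d would then test people on something the form does not contain. If the form carries the clause too, both need correction.

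**Conclusion.** The concern holds. The pill clause in item d is current, operative text, and the design, schedule, procedures, risks and benefits all contradict it. It must be corrected, because it puts a false treatment benefit into the consent and capacity step for adults with intellectual disability.

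The conclusion rests on the text alone. It depends neither on the illustrative count (about 11 to 32 of an assumed 42 evaluable participants aged 18–20) nor on how the clause came to be there. Eligibility, measurements, sample size and analysis are unaffected.

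**What to change.** Delete the pill clause from section 8.5.1, item d. Replace it with the benefits in section 8.3.4: the tests may find an abnormality such as diabetes, dyslipidemia or hypothyroidism, with results passed on and referral where appropriate; the visit may raise awareness of healthy diet and exercise; and there may be no direct benefit. Then check the consent form and the picture book for the same statement and correct them if it is there.

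As optional tidying, correct the treatment or intervention wording in sections 4.3, 7.2, 8.3.1 and 8.3.3.

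The cost is a wording amendment to one item, up to four further phrases, and a check of two participant documents. No procedure, sample size or analysis changes.
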